5.3 Study Drugs

5.3.1 Blinatumomab

Blinatumomab will be administered as a continuous IV infusion over four weeks followed by a two-week treatment-free interval. It is recommended that patients are hospitalized at least during the first 14 days of the first cycle and the first two days of the subsequent cycles. The hospitalization time depends on the investigator's judgment, as well as safety and tolerability of blinatumomab.

Cycle 1: The planned initial dose of blinatumomab is 9 µg/day administered via continuous intravenous infusion on days 1-7 of the first 42-day cycle. If patients tolerate the initial infusion without significant adverse events, then the dose of blinatumomab will be escalated to 28 µg/day administered via continuous intravenous infusion on days 8-28 of cycle 1. There will be a minimum blinatumomab treatment-free interval of 14 days following the completion of blinatumomab infusion prior to the initiation of the next cycle. Patients will be eligible for up to five cycles of blinatumomab if they achieve complete remission (CR) or CR with incomplete hematologic recovery (CRh) following 1-2 cycles of treatment. Given that this is a group of patient with a very high risk ALL, patients will be eligible to proceed to allogenic HSCT at the treating physician's discretion at any time after a response is documented. For patients receiving **cycles 2-5**, the planned dose of blinatumomab is 28 µg/day to be administered via continuous infusion on days 1-28 of each 42-day cycle.

Blinatumomab should be infused at a constant flow rate using an infusion pump. The pump should be programmable, lockable, non-elastomeric, and have an alarm. Blinatumomab infusion bags should be infused over 24 or 48 hours according to the instructions on the pharmacy label on the bags (Section 8.1.1). The solution should be administered using IV tubing that contains a sterile, non-pyrogenic, low protein-binding, 0.2 micron in-line filter. The IV line should never be flushed, especially when changing bags or at the completion of infusion, due to the risk of excess dosage. Blinatumomab should be infused through a dedicated lumen. Nivolumab +/- ipilimumab will be infused through a separate line from blinatumomab to allow continuous blinatumomab infusion when nivolumab +/- ipilimumab are administered.

Blinatumomab is known to cause cytokine release syndrome (CRS). To reduce the incidence of CRS associated with blinatumomab administration, all patients will be pre-medicated with dexamethasone 20 mg to be given intravenously one hour prior to the initiation of blinatumomab on day 1 of each cycle, prior to a step dose escalation (such as cycle 1 day 8), or when restarting an infusion after an interruption of 4 hours or more.

5.3.2 Nivolumab

Nivolumab will be given every two weeks (± 2 days) at a dose of 80 or 240 mg for up to 1 year. Nivolumab administration starts on day 11 of cycle 1; however, the first dose of nivolumab may be delayed up to 4 days (until day 15) in cycle 1 if necessary to allow resolution of any adverse events associated with blinatumomab administration. If the delay is more than 4 days then the nivolumab should be administered at the next scheduled time (day 25 ± 2 days of cycle 1). Patients may be dosed no less than 12 days from the previous dose of drug. Patients may continue on nivolumab for up to one year from the start of treatment on the study if they achieve CR or CRh following 1-2 cycles of treatment.

Nivolumab is to be administered as IV infusion over approximately 30 minutes, using a volumetric pump with a 0.2/1.2-micron low protein binding (polyethersulfone membrane) in-line filter at the protocol-specified dose. The drug can be diluted with 0.9% normal saline or D5W for delivery but the total drug concentration of the solution cannot be below 0.35 mg/mL. It is not to be administered as an IV push or bolus injection. At the end of the infusion, flush the line with a sufficient quantity of normal saline. Nivolumab will be administered through a separate line from blinatumomab to allow continuous blinatumomab infusion during nivolumab administration. A flat dose of 240 mg can be infused undiluted or diluted so as not to exceed a total infusion volume of 120 mL.

For nivolumab and ipilimumab combination studies see section 5.3.4.

5.3.3 Ipilimumab

Ipilimumab will be given at a dose of 1 mg/kg every 6 weeks. Patients may be dosed no less than 38 days from the previous dose of drug. Ipilimumab administration starts on day 11 of cycle 1; however, the first dose of ipilimumab may be delayed up to 4 days (until day 15) in cycle 1 if necessary to allow resolution of any adverse events associated with blinatumomab administration. If the delay is more than 4 days and as the goal is to administer ipilimumab and nivolumab on the same day, then the ipilimumab should be administered at the next scheduled time of nivolumab administration (day 25 ± 2 days). Patients may continue on ipilimumab for up to one year from the start of treatment on the study if they achieve CR or CRh following 1-2 cycles of treatment.

The dosing calculations should be based on the actual body weight. If the subject's weight on the day of dosing differs by $>10\%$ from the weight used to calculate the original dose, the dose must be recalculated. All doses should be rounded to the nearest milligram or as per institutional guidelines. There will be no dose modifications allowed.

Study drug is to be administered as an IV infusion using a volumetric pump through an in-line, sterile, non-pyrogenic, low-protein-binding filter with a pore size of 0.2 micrometer to 1.2 micrometer.

The infusion should be administered over approximately 90 minutes, followed by a normal saline

(NS) flush with an adequate amount of NS to completely flush the residual fluid (dead space) in the administration set (approximately 30 - 50 mL). Ipilimumab will be administered through a separate line from blinatumomab to allow continuous blinatumomab infusion during ipilimumab administration.

5.3.4 Nivolumab with Ipilimumab

Nivolumab and ipilimumab should be given on the same day, whenever possible. If one medication needs to be held/delayed, the other medication should ideally be held as well to allow concurrent dosing.

When infusions of ipilimumab and nivolumab are given on the same day, the preferred treatment is to give nivolumab followed by ipilimumab.

Toxicity management for the combined agents follows the same template guidelines and algorithms that are provided in Section 6.3 and Appendix D for single agent nivolumab.

Follow the same infusion timing guidelines: nivolumab over 30 minutes and ipilimumab over 90 minutes. The length of each cycle and the number of cycles or doses should be explained clearly.

When both nivolumab and ipilimumab are to be administered on the same day, separate infusion bags and filters must be used for each infusion. Nivolumab is to be administered first. The nivolumab infusion must be promptly followed by a saline flush to clear the line of nivolumab before starting the ipilimumab infusion.

5.4 Definition of Dose-Limiting Toxicity

Dose-limiting toxicity (DLT) will be assessed for the first cycle of treatment (6 weeks/42 days) at all dose levels.

A DLT is considered a treatment-related toxicity. Subjects who are withdrawn from the study before the completion of the DLT evaluation period in any phase for a reason other than a DLT will be replaced (NOTE: This includes subjects who may be removed during the blinatumomab-only run-in phase, prior to addition of nivolumab/ipilimumab). A toxicity with a clear etiology NOT related to a study treatment agent may not be considered a DLT; the Protocol Chair should be consulted in all cases.

DLTs include any grade 3 or higher non-hematologic toxicities which requires a subject to permanently discontinue protocol treatment during the DLT period as defined in Section 6.2.2 and 6.3.4 with the following exceptions:

- A) Any grade 3 or 4 drug-related laboratory abnormality or electrolyte abnormality that can be managed with electrolyte replacement, hormone replacement, insulin or that does not require treatment discontinuation
- B) Any grade 3 or higher toxicities that are frequent in ALL population such as fever, infection, bleeding, fatigue, bone pain, disseminated intravascular coagulation, tumor

lysis syndrome. Grade 4 infections which are felt by the PI to be primarily related to nivolumab ± ipilimumab administration or may have been exacerbated by nivolumab ± ipilimumab administration will be considered DLT. The PI and study team will closely monitor the cumulative rate of infections through the trial and in the expansion cohort to see whether the rate is higher than expected with blinatumomab alone.

- C) Any grade 3 or 4 event that occurs during the blinatumomab run-in period prior to the initiation of nivolumab or ipilimumab and requires permanent treatment discontinuation will not be considered a DLT. During the phase II trial based on which blinatumomab received FDA approval, 10% of patients permanently discontinued blinatumomab due to adverse events that were thought to be treatment-related and 18% of patients discontinued treatment due to adverse events.³² Thus adverse events requiring treatment discontinuation due to blinatumomab monotherapy are common and expected, so they should not be defined as DLTs in a trial to assess combination therapy.

For hematologic toxicity, the only adverse event that will be considered dose limiting is:

Grade ≥ 4 neutropenia or thrombocytopenia with a hypocellular bone marrow and no evidence of residual leukemia lasting for >42 days. Given that severe anemia, neutropenia and thrombocytopenia are features of advanced ALL and commonly encountered in this patient population, they will not be used to define DLT except if associated with prolonged treatment-associated aplasia as described above.

Management and dose modifications associated with the above adverse events are outlined in Section 6. Dose delay would be permitted as indicated in Section 6.

Dose escalation will proceed within each cohort according to the following scheme. Dose-limiting toxicity (DLT) is defined above.

Number of Patients with DLT at a Given Dose Level	Escalation Decision Rule
0 out of 3	Enter 3 patients at the next dose level.**
≥ 2	Dose escalation will be stopped. This dose level will be declared the maximally administered dose (highest dose administered). Three (3) additional patients will be entered at the next lowest dose level if 0 or 3 patients were treated previously at that dose.
1 out of 3	Enter at least 3 more patients at this dose level. 
 • If 0 of these 3 patients experience DLT, proceed to the next dose level. • If 1 or more of this group suffer DLT, then dose escalation is stopped, and this dose is declared the maximally administered dose. Three (3) additional patients will be entered at the next lowest dose level

	if only 3 patients were treated previously at that dose.
≤1 out of 6 at highest dose level below the maximally administered dose	This is generally the recommended phase 2 dose. At least 6 patients must be entered at the recommended phase 2 dose.
**For dose levels A1 and A-1 (if necessary), six total patients will be enrolled even if there are no toxicities among the first three patients	

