13.4.1 Dose Expansion

Continuous monitoring of safety will be completed during the enrollment and treatment period of each expansion cohort. If it becomes evident that the proportion of patients experiencing a treatment-related toxicity meeting DLT criteria convincingly exceeds 30%, the study will be halted for a safety consultation. The toxicity stopping rule will hold enrollment if the posterior probability of failure being larger than 0.30 is 70% or higher. The prior for this monitoring rule is beta (1,2). This means that our prior guess at the proportion of failures is 33%, and there is 90% probability that this proportion is between 2.5% and 77.6%. The monitoring rule and operating characteristics are given below.

- Stop if 2 out of 2 patients experience a DLT: $\Pr(\text{Risk} > 0.3 \mid \text{Data}) = 0.916$
- Stop if 2 out of 3 patients experience a DLT: $\Pr(\text{Risk} > 0.3 \mid \text{Data}) = 0.837$
- Stop if 2 out of 4 patients experience a DLT: $\Pr(\text{Risk} > 0.3 \mid \text{Data}) = 0.744$
- Stop if 3 out of 5 patients experience a DLT: $\Pr(\text{Risk} > 0.3 \mid \text{Data}) = 0.874$
- Stop if 3 out of 6 patients experience a DLT: $\Pr(\text{Risk} > 0.3 \mid \text{Data}) = 0.806$

Operating Characteristics of stopping rule for toxicity, based on 5000 simulations:

True Toxicity Rate	Probability of declaring treatment too toxic	Average sample size
20%	17%	3.9
25%	26.8%	3.8
30%	34.6%	3.7
35%	43.1%	3.6
40%	52.7%	3.5
45%	61%	3.4
50%	68.8%	3.2

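### Exception B in 5.4 has no upper grade limit, so read literally a treatment-related death from infection, bleeding, DIC or tumor lysis after combination therapy starts is not a DLT

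*Combined protocol and SAP*

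**What the plan says.** The general rule in 5.4 is broad: "DLTs include any grade 3 or higher non-hematologic toxicities which requires a subject to permanently discontinue protocol treatment during the DLT period". Three exceptions follow, with different grade ranges.

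- Exception A covers "Any grade 3 or 4 drug-related laboratory abnormality or electrolyte abnormality" that can be managed or does not require stopping.
- Exception B covers "Any grade 3 or higher toxicities that are frequent in ALL population such as fever, infection, bleeding, fatigue, bone pain", and its list goes on to "disseminated intravascular coagulation, tumor" lysis syndrome. It then adds back "Grade 4 infections which are felt by the PI to be primarily related to nivolumab ± ipilimumab administration", or which those agents may have made worse.
- Exception C covers "Any grade 3 or 4 event that occurs during the blinatumomab run-in period prior to the initiation of nivolumab or ipilimumab".

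Section 5.4 also says that a subject withdrawn in the DLT period for a reason other than a DLT is replaced, in any phase. Section 13.2 admits a subject to the DLT evaluation set in three ways: finishing 6 weeks without a DLT, having a DLT, or being withdrawn because of one. The expansion rule in 13.4.1 acts if "the proportion of patients experiencing a treatment-related toxicity meeting DLT criteria convincingly exceeds 30" percent, so it uses the same definition, as does the 30% trigger in 5.2.2.

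**The concern.** A and C name grades 3 and 4 only. B starts at grade 3 and has no ceiling, so it takes in grade 5. The add-back names grade 4 infections and nothing else. Literally, a life-threatening infection attributed to nivolumab is a DLT, but the same infection is not one if it kills the patient. For bleeding, DIC and TLS no fatal event is added back at all.

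The DLT count decides whether a dose level is called the MTD and whether expansion is held. In a trial whose primary objective is safety, a related toxic death is the event that the count should least be able to miss.

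**Working it through.** **1. Does any other section make a related death a DLT?**

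| Section | What it does with the death | Makes it a DLT? |
|---|---|---|
| 5.4, Protocol Chair consultation | Attached to toxicities with a clear cause other than study treatment | No |
| 5.4, hematologic rule | Prolonged aplasia is the only hematologic DLT, so reclassifying DIC or bleeding does not help | No |
| 5.4, infection-rate monitoring | No threshold or consequence; omits bleeding, DIC and TLS | No |
| 5.6 and 5.8 | Death ends treatment and study participation | No |
| 7.3.3 | Death must be reported, whatever the cause | No |
| 12.1 | Calls at least monthly; sign-off on escalation decisions | No |
| 13.4.2 | Mortality rule, after transplant only | No |

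The drafters do cap at grade 4 where they mean to: in A, in C, and in the 7.3.4 reporting exclusions for infections and TLS. The open range in B therefore cannot simply be read as capped.

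**2. What happens to the patient?** A cycle 1 death from an exempt event meets none of the three criteria in 13.2, and 5.4 calls for replacement. The death leaves both numerator and denominator.

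**3. Can one event change a decision?** In escalation, 1 of 6 passes and 2 of 6 does not. For expansion, the 13.4.1 prior is beta(1,2), so with x DLTs in n patients the posterior is beta(1+x, 2+n−x), and enrollment holds if P(risk > 0.30) is at least 0.70. This reproduces the plan's figures: 2/2 = 0.916, 2/3 = 0.837, 2/4 = 0.744, 3/5 = 0.874, 3/6 = 0.806. One event fewer gives 0.420 at 1/4 and 0.552 at 2/6, and the cohort continues.

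**4. Illustrative size.** The rates are assumptions. Let c be the per-patient risk of a counted DLT and f the risk of an exempt related death.

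- Deaths uncounted and replaced: effective rate p = c/(1−f).
- Deaths counted: p = c + f.
- Pass: P(at most 1 of 6) = (1−p)^6 + 6p(1−p)^5.
- Hold, from the listed boundaries (2 events by patient 4, or 3 by patient 6): P(at least 2 of 4) + P(exactly 1 of 4) × p².

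| c + f | Handling | p | Pass | Hold |
|---|---|---|---|---|
| 20% + 5% | uncounted | 0.20/0.95 = 0.211 | 0.242 + 0.387 = 0.63 | 0.197 + 0.018 = 0.22 |
| 20% + 5% | counted | 0.250 | 0.178 + 0.356 = 0.53 | 0.262 + 0.026 = 0.29 |
| 20% + 10% | uncounted | 0.20/0.90 = 0.222 | 0.221 + 0.380 = 0.60 | 0.216 + 0.021 = 0.24 |
| 20% + 10% | counted | 0.300 | 0.118 + 0.303 = 0.42 | 0.348 + 0.037 = 0.39 |

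The hold figures are exact for the listed boundaries. The simulated table in 13.4.1 is a few points lower (26.8% at a 25% rate, 34.6% at 30%). The uncounted hold figures assume that replacement also applies in expansion; without it, p = 0.20 and the hold probability is 20% in both scenarios.

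**The case against.** The drafters almost certainly did not mean to exempt toxic deaths. An investigator who must count a grade 4 infection that nivolumab may have worsened is unlikely to leave out the same infection once fatal. A death would also be seen at once, through expedited reporting and the calls with the CTEP medical officers. This bears on how likely the error is in practice. It does not repair the text, because none of these steps feeds the counts, and the infection argument does not reach bleeding, DIC or TLS.

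The death rates have no source in the documents and produce the whole effect. That stands: the figures show direction and sensitivity, not an expected loss.

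Three stronger readings are tempting, and the documents do not support them.

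- *That the A1 result is wrong.* Section 5.2.1 reports 1 DLT in 6 and mentions no such death.
- *That exempting grade 4 bleeding, DIC and TLS is also an error.* The protocol gives its reason, that these events are frequent in ALL. Table 6.2 holds and resumes blinatumomab after a first grade 3-4 DIC, so many such events would not meet the general DLT rule anyway. This is a stated design choice.
- *That the patient who died stays among the six as a non-DLT.* That would put the pass probability at 66% (p = 0.20) and widen the gap, but 5.4 and 13.2 remove the patient from the evaluable set.

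**Conclusion.** The point holds on the wording. A treatment-related fatal infection, bleed, DIC or TLS after combination therapy starts falls within exception B, is not added back, leads to replacement, and is invisible to both decision rules. This is a stated rule that gives the wrong count, rather than a missing detail.

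Under the assumed rates, leaving such deaths uncounted raises the chance that a dose level passes by about 10 points (20% + 5%) or 18 points (20% + 10%), and lowers the chance of an expansion hold by about 7 or 15 points. These figures rest on the assumed rates, on independent patients, and on replacement in both phases. Because the gap sits in the definition behind the primary safety endpoint and is cheap to close, it should be fixed.

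**What to change.** In 5.4, limit exception B to grades 3 and 4, matching A and C. Add one sentence: a grade 5 event that begins after nivolumab or ipilimumab has started, and is at least possibly related to study treatment, counts as a DLT in escalation and in expansion monitoring. Align the evaluable-set wording in 13.2 and the monitoring rule in 13.4.1 with that sentence.

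Leave the exemption of non-fatal background ALL events and exception C's run-in rule as they are. Since C names only grades 3 and 4, the added sentence should also state how a death in the blinatumomab-only run-in is classified, so that capping B does not change this by accident.

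The cost is an occasional extra DLT, including some deaths of uncertain attribution and some due to blinatumomab alone after day 11. With only one DLT tolerated in six, a misattributed death could stop a tolerable dose level. The sponsor should accept that trade openly.

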5.5 General Concomitant Medication and Supportive Care Guidelines

Because there is a potential for interaction of blinatumomab, nivolumab, and ipilimumab with other concomitantly administered drugs, the case report form must capture the concurrent use of all other drugs, over-the-counter medications, or alternative therapies. The Principal Investigator should be alerted if the patient is taking any agent known to affect or with the potential for drug interactions. The study team should check a frequently-updated medical reference for a list of drugs to avoid or minimize use of. [Appendix B](#) (Patient Drug Information Handout and Wallet Card) should be provided to patients if available.

5.5.1 Supportive Care Guidelines

In general, concomitant medications and therapies deemed necessary for the supportive care and safety of the subject are allowed, provided their use is documented in the medical records and meets the dose modification guidelines outlined in Section 6. The administration of any other therapies intended to treat the primary condition including chemotherapy and biologic agents is NOT permitted. Similarly, the use of other concurrent investigational drugs is not allowed.

5.5.2 Permitted Concomitant Medications

- **Corticosteroids:** Inhaled or topical steroids and adrenal replacement doses ≤10 mg daily prednisone equivalents are permitted in the absence of active autoimmune disease. Subjects are permitted to use topical, ocular, intra-articular, intranasal, and inhalational corticosteroids (with minimal systemic absorption). Physiologic replacement doses of systemic corticosteroids are permitted, even if ≥10 mg/day prednisone equivalents. A brief course of corticosteroids for prophylaxis (e.g., contrast dye allergy), for treatment of non-autoimmune conditions (e.g., delayed-type hypersensitivity reaction caused by contact allergen), treatment of toxicities (e.g., cytokine release syndrome or neurologic toxicity due to blinatumomab or autoimmune toxicities caused by ipilimumab or nivolumab), and for treatment of infusion reactions and premedication (i.e. 20 mg of dexamethasone prior to blinatumomab initiation and step doses, and prior to re-initiating infusion if interrupted for ≥4 hours) is permitted. Additionally, prephase treatment with dexamethasone 10 mg/m² (maximum total 24 mg per day) for up to 5 days is required with bone marrow blasts more than 50%, peripheral blood blasts of 15,000/μL or higher, or elevated lactate dehydrogenase suggesting rapidly progressing disease as per investigator's assessment to reduce the tumor burden and mitigate the potential for cytokine release syndrome unless other acceptable cytoreductive measures, as written in

3.2.1 and 5.1 have previously been employed. There is a published case report suggesting that for cases of life-threatening cytokine release syndrome for which dexamethasone and supportive care measures are not adequate, consideration may be given to the administration of tocilizumab, the anti-IL-6 monoclonal antibody.⁹⁰

